## Frailty Assessments:

We will evaluate frailty based on a validated scoring system^1 that characterizes frailty as an age-associated decline in 5 domains: shrinking, weakness, exhaustion, low physical activity, and slowed walking speed.

These measurements are described below based on the original paper.

Each domain will yield a dichotomous score of 0 or 1. We will classify patients scoring 3 to 5 as frail, 1 to 2 as intermediately frail (pre-frail), and 0 as nonfrail. We will also measure the Instrumental Activities of Daily Living scale as part of the frailty assessment. Research staff will undergo frailty screen training to allow consistent measurements of frailty domains in the study population. Frailty assessment will be held in clinic during the patient's preoperative and postoperative visits, and again at the time of the 1 year follow-up visit.

**Weight loss:** "In the last year, have you lost more than 10 pounds unintentionally (i.e., not due to dieting or exercise)?" If yes, then frail for weight loss criterion.

### **Exhaustion:**

Using the CES-D Depression Scale, the following question and the accompanying two statements are read:

"How often in the last week did you feel this way?" (a) I felt that everything I did was an effort (b) I could not get going.

The subject will respond to these questions using the following scale:

- 0 = rarely or none of the time (1 day);
- 1 = some or a little of the time (1–2 days);
- 2 = a moderate amount of the time (3–4 days); or

3 = most of the time.

Subjects answering "2" or "3" to either of these questions are categorized as frail by the exhaustion criterion.

**Physical Activity:**

Based on the short version of the Minnesota Leisure Time Activity questionnaire, asking about walking, chores (moderately strenuous), mowing the lawn, raking, gardening, hiking, jogging, biking, exercise cycling, dancing, aerobics, bowling, golf, singles tennis, doubles tennis, racquetball, calisthenics, swimming. Kcals per week expended are calculated using standardized algorithm. This variable is stratified by gender:

*Men:* Those with Kcals of physical activity per week <383 are frail. *Women:*

Those with Kcals per week < 270 are frail.

**Walk Time:** Table 3 (below) will be used to stratify Walk Time by gender and height (gender-specific cutoff a medium height).

**Table 3. Walk Time criteria for frailty**

Gender	Cutoff time to walk 15 feet criteria for frailty
Men	
Height ≤ 173 cm	≥ 7 seconds
Height > 173 cm	≥ 6 seconds
Women	
Height ≤ 159 cm	≥ 7 seconds
Height > 159 cm	≥ 6 seconds

**Grip Strength:** Table 4(below) will be used to stratify Grip Strength by gender and body mass index (BMI) quartiles

**Table 4. Grip Strength criteria for frailty**

Gender	Cutoff for grip strength (Kg) criterion for frailty
Men	
BMI ≤ 24	≤ 29
BMI 24.1–26	≤ 30
BMI 26.1–28	≤ 31
BMI > 28	≤ 32
Women	
BMI ≤ 23	≤ 17
BMI 23.1–26	≤ 17.3
BMI 26.1–29	≤ 18
BMI > 29	≤ 21

Instrumental Activities of Daily Living Scale will be used to provide additional information on functional status in the frailty assessment. Seven questions are asked to gauge participant difficulty with using the telephone, walking, preparing meals, managing money, shopping, doing housework, and taking medicines.

Each study subject will participate in the study for approximately 1 year.

Consent will be obtained before any study related events occur. Cognitive and quality of life testing, medical history, TCD measurements (to determine subject eligibility), National Institutes of Health Stroke Scale (NIHSS), ECG and psychomotor testing and Brief Smell Identification Test will be performed within 1- 2 weeks before surgery. We plan to perform this testing in the outpatient center for most patients. Patients who are in-patients prior to surgery will have testing performed on the hospital ward.

On the day of surgery after anesthesia induction the patients will be connected to a transcranial Doppler to monitor middle cerebral artery blood flow velocity and to a near infra-red spectroscopy machine to monitor cerebral oxygenation. Doppler probes are held in place with a fitted head band. The NIRS electrodes will be placed using manufacturer guidelines. Both devices are FDA approved. Transcranial Doppler and NIRS are used to monitor cerebral blood flow autoregulation. Subject randomization will also be done at this time.

Before cardiopulmonary bypass is initiated (after sternotomy and pericardiotomy) the patients will undergo epiaortic ultrasound examination of the ascending aorta to examine for atherosclerotic changes. In many centers epiaortic ultrasound has replaced the traditional palpations by the surgeon of the aorta for the detection of atherosclerosis of the ascending aorta.

The day of surgery during cardiopulmonary bypass the patients will undergo cerebral blood flow autoregulation monitoring using methods described in the preliminary data section. For individuals in the intervention arm, blood pressure targets during cardiopulmonary bypass will be determined by this monitoring and will be the blood pressure where the mean velocity index (Mx) is <0.2 or the cerebral oximetry index (COx) is < 0.3. This information will be communicated to the perfusionist, anesthesiologist and surgeon by the investigative team. In the control arm, cerebral blood flow autoregulation information will be monitored and saved but the data will not be provided to the surgical team.

After surgery, visits will all be done in the ICU or postoperative unit. The patients will have an ECG which is to be done upon the subject's arrival in the ICU after surgery. This procedure is routine care and only a copy of the ECG will be obtained for the study case report form.

Each patient will be evaluated daily by the attending and resident physicians. Data will be collected from the patient record by a member of the study team. Every patient will have an ECG done each day postoperative days 1 through 3, per standard of care. An MRI will be done at some point between postoperative day three and postoperative day 14 or at hospital discharge (whichever occurs first). In addition, all patients will be evaluated between postoperative days 5 and 7 or at hospital discharge (whichever occurs first) with the National Institutes of Health Stroke Scale (NIHSS) And Brief Smell Identification Test.

Cognitive testing and the Brief Smell Identification Test will be repeated at the time the patient returns for follow-up with the cardiac surgeon, about 4 to 6 weeks postoperatively.

Cognitive testing will be repeated at 1 year postoperative.

### Assessment Schedule

The schemata of study procedures are listed in Table 5.

Assessment Schedule	PRE-OP	DOS before CPB	DOS CPB	DOS after CPB	ICU	POD 1	POD 2	POD 3	POD 4	POD 5-7	4-6 wks POST-OP	1 YEAR POST-OP
Informed consent	X											
Medical history/PE	X											
NIH Stroke Scale	X									X	X	X
Smell Test	X									X	X	
Psychometric and quality of life testing	X									X	X	
Frailty testing	X										X	X
Urine pregnancy test	X											
SAEs/AEs												
Randomization		X										
Mx and CO 2 monitoring		X	X	X								
Bispectral Index Monitoring		X	X	X								
Urine Flow		X	X	X								
Brain MRI										X 1		
MMSE and Abbreviated Digit Span	X											
Delirium assessments						X	X	X	X			
Electrocardiogram	X				X	X	X	X				

**PRE-OP** = preoperatively (up to 2 weeks before surgery); **DOS** = day of surgery; **POD** = postoperative day; **POST-OP** = postoperatively; **SAE** = serious adverse event; **AE** = adverse event; 1 = MRI will be done once between post-op day 3 and post-op day 14; 2 = blood drawn for standard of care ACT measurements that would normally have been discarded will be used for these samples; 3 = a 3mL lavender top vacutainer tube will be drawn in the morning of POD1 at the same time standard of care bloods are drawn; 4 = urine pregnancy test will be done on women of childbearing potential only; 6 = Delirium assessments will be done on 3 of the first 4 postoperative days; 7 = urine flow will be monitored during surgery.

Clinicians caring for the patients will participate in managing blood pressure in the Blood Pressure Intervention Group and, thus, cannot be blinded. Individuals making the neurologic assessments and performing data analysis will be blinded to the intraoperative management group, providing effective double blinding.

Participation in this study will not require discontinuation of a subject's current therapy any more than would be required if the subject were to undergo CABG and/or valve surgery outside of the study. The Control Group will receive standard care practiced here at Northwestern Memorial Hospital. The Blood Pressure Intervention Group will be receiving investigational care. Blood pressure targets during surgery will be at least those of the standard care group or higher based on the individualized autoregulation measurements.

**Justification for inclusion of a placebo or non-treatment group.**

There will be a Control Group in which mean arterial pressure is maintained during surgery, including CPB, using institutional standard of care. This is being done in order to allow direct comparison of the current standard of care with the Blood Pressure Intervention Group.

**Definition of treatment failure or participant removal criteria.**

There is no definition for treatment failure. The subject will be excluded from further study if an adequate temporal window for TCD monitoring cannot be identified before surgery.

**Description of what happens to participants receiving therapy when study ends or if a participant's participation in the study ends prematurely.**

If a subject's participation in the study were to end prematurely then that subject would be treated according to current standard of care.

## **Study Statistics**

a. Primary outcome variable.

**Aim 1:** *To determine whether targeting blood pressure to a level above an individual's lower CBF autoregulatory threshold during CPB reduces the frequency of the composite end point of clinical stroke, a diffusion-weighted MRI brain lesion, or postoperative cognitive decline 4 to 6 weeks after surgery, compared with patients who receive standard blood pressure management.*

**Aim 1a:** *To assess whether extracranial and/or intracranial arterial stenosis (detected by MR angiography), or other patient characteristics such as age, gender, hypertension, diabetes, or prior stroke, modify the effect of maintaining blood pressure above an*

*individual's lower CBF autoregulatory threshold on the risk for the above composite neurological outcome.*

**Aim 1b: To assess whether targeting MAP to a level above an individual's lower CBF autoregulatory threshold during CPB reduces the frequency of cognitive decline 1 year after surgery compared with the use of standard blood pressure management.** In Aim 1, we will test whether the Intervention and Control groups have the same risk of the primary composite neurologic endpoint of stroke, DWI lesion, or cognitive decline 4 to 6 weeks after surgery (i.e., null hypothesis). This will be done using a two-sided test of proportions at 5% significance level. We will first calculate and report the relative risk (RR) of composite neurologic outcome by comparing the Intervention and Control groups without adjusting for any potential confounders (i.e., the unadjusted RR). In addition, we will construct an adjusted estimate of RR using a generalized linear model (GLM) with Poisson distribution and robust standard errors. The candidate models will include study group as the primary independent variable as well as extra- or intracranial arterial stenosis determined by MRA, patient age, gender, and baseline risk factors that are assumed to be highly predictive of the outcome, such as history of hypertension, diabetes, or prior stroke. To assess potential effect modification by cerebral arterial stenosis, age, gender, hypertension, diabetes, or prior stroke (Aim 1a), we will calculate the unadjusted RR stratified by these variables. We will use a test of homogeneity to compare stratum-specific estimates of RR. Finally, we will use the model developed in Aim 1 to report stratum-specific adjusted estimates of RR by introducing appropriate interaction terms of these variables and study group in the GLM model. We will compute the Z-score for the cognitive tests to normalize the distribution to the control data. The individual Z-scores will be combined into an average score and re-normalized. To assess postoperative change in cognitive function for up to 1 year (Aim 1b), we will use population-average marginal models estimated using generalized estimating equations (GEE) with exchangeable working correlation structure. The model will include assessment time with 2 indicator variables for 1 year and 4 to 6 weeks postoperation and baseline as the reference group as well as Intervention Group, and their interaction to test whether postoperative trajectory of cognitive function differs by group.

As a secondary analysis, we will develop logistic regression models on the binary outcome of the composite neurologic outcome and the time spent below the CBF autoregulatory threshold regardless of treatment assignment (i.e., data combined from both groups), while adjusting for other statistically and scientifically important covariates. This will allow for the development of a "dose-response" relationship between blood pressure below the CBF autoregulatory threshold and outcome, whereby we can estimate the probability of an adverse neurologic event as a function of time spent in suboptimal perioperative conditions. In this analysis, we will consider the time spent below the CBF autoregulatory threshold as both an absolute time in minutes and as a percent of the total time on bypass, thereby allowing us to determine which measure of time below optimal threshold is more predictive of an adverse outcome. Note, the lower graph in **Figure 6 (above)**, depicts the data from a single patient showing the percent time at each blood pressure epoch. The program saves the data in a spreadsheet format.

As an additional set of analyses for the multivariable logistic regression models, we will look whether there are interactions (e.g., effect modification) between gender or extra- and intra-cranial arterial stenosis on the composite neurologic outcome. In considering patient sex, we are particular interested in whether or not the effectiveness of the intervention applies equally to women as well as men. Similarly, we are interested in determining whether the association between the intervention and the neurologic end point differs in the presence or absence of clinically significant narrowing in the arteries of the neck and head. In considering the modifying effect of carotid arterial stenosis, we will dichotomize this variable with the cut point of <70% versus  $\geq 70\%$  narrowing based on the NASCET criteria, using the methods for measurement described in **Magnetic Resonance Imaging**. For intracranial arterial stenosis, we will dichotomize the stenosis as  $\geq 50\%$  or <50%. As a second step, we will also consider three categories of arterial stenosis (<50%, 50%–70%, and >70%), which considers the clinically important stenosis definition as defined by the Warfarin-Aspirin Symptomatic Intracranial Disease criteria. Interaction terms for both the binary definition of stenosis and the three categories of stenosis will be incorporated into the regression model, and any statistically significant effect modifications will be determined via standard Wald tests. Finally, we will also consider arterial stenosis in the multivariable logistic regression model as a continuous variable if the inter-rater reliability is high for this variable. Considering arterial stenosis as a continuous variable will allow us to consider possible thresholds of risk for the neurologic end point as a function of a continuous measure of stenosis. We will look for inflection points in the risk of stenosis on the outcome by incorporating linear (e.g., broken arrow regression) and cubic spline terms in the model. If the inter-rater reliability for the continuous measures of stenosis is low, we will consider only the above categories of mild, moderate, and severe stenosis in the regression models.

**Aim 2:** *To compare the accuracy of CBF autoregulation as determined by monitoring of the linear regression correlation between blood pressure and cerebral O2 saturation (cerebral oximetry index) and near-infrared reflectance spectroscopy (hemoglobin volume index) with the accuracy of that determined by TCD-measured CBF velocity (mean velocity index).*

We expect that the estimated lower CBF autoregulatory thresholds based on the cerebral oximetry index will be similar to those measured with both the mean velocity index and the hemoglobin volume index. Nevertheless, to quantify variance, we will first calculate the pair-wise differences in each of these estimate threshold levels per patient. Graphically, we will quantify these differences using histograms to assess the distribution of the discrepancy. In addition, we will create Bland-Altman plots to investigate if these differences are related to the absolute values of the threshold estimate. In other words, does this difference in estimates using either the hemoglobin value and cerebral oximetry or the mean velocity index and the cerebral oximetry increase (decrease) as one's autoregulatory threshold increases (decreases)? We will also investigate whether the discrepancies in threshold estimates differ by the demographic or clinical variables in our patient sample using both univariate methods and linear regression modeling to examine the effect of these covariates on discrepancies in threshold estimates.

This hypothesis has already been adequately addressed and will no longer be an aim of this study as we move forward.

**Aim 3:** *To perform secondary analysis to determine whether an association exists between abnormal perioperative TCD findings indicative of intracranial arterial stenosis and the risk for the composite neurologic outcome.*

Under this aim, we will assess whether perioperative TCD findings indicative of arterial stenosis of major cerebral vessels (see **Transcranial Doppler Evaluation**) are predictive of the composite adverse postoperative neurologic outcome. We will test for this possible association by considering - in the multivariable logistic regression model described under Specific Aim 1 - a dummy variable indicative for a positive finding for stenosis preoperatively. Results from this model in conjunction with determination of any potential effect modifications of stenosis on the outcome as described under **Aim 1a** will serve as a valuable tool for assessing the benefits and risks of this CBF-targeted intervention during CPB on patients found to have clinically significant narrowing of the intracranial arteries, as determined by either MRA or TCD examination before surgery.

**Aim 4:** *To assess whether targeting MAP during CPB to a level above an individual's lower CBF autoregulatory threshold during CPB reduces the frequency of postoperative delirium, as assessed with a structured examination, compared with the use of standard blood pressure management.*

In **Aim 4**, we will compare Intervention and Control groups for proportion of patients with delirium. For the analysis, we will include only those patients who have undergone the more extensive delirium assessments as described in this proposal. This same structure assessment for delirium was initiated in year 4 of the prior grant and is consistent with other delirium studies performed by co-investigators (R01 AGO33615). We will estimate the unadjusted (without any other variable in the model) and adjusted RR of delirium by comparing the two study groups. We will adjust for potential confounders using a generalized linear regression model with Poisson distribution and robust standard errors.

**Aim 5:** *To determine whether baseline frailty is independently associated with delirium or functional decline after cardiac surgery.*

In **Aim 5**, we will test the hypothesis that frailty is associated with postoperative delirium. The primary outcome will be the development of delirium at any time, as measured by CAM or CAM-ICU and coded as a binary variable. Secondary outcomes will be delirium severity from the DRS-R-98 scale. Bivariable and multivariable logistic regression analysis will be used to determine if frailty is associated with postoperative delirium. We will also test the hypothesis that frailty is associated with decreased function after cardiac surgery. The primary outcome will be proportion of patients with >1 IADL decline. Secondary outcomes will be change in gait speed and grip strength. Bivariable and multivariable linear and logistic regression analyses will be used. For each of these analysis, covariates to include in the model will be selected using a priori evidence, and may include age, gender, race, baseline cognitive status, education, medications, and

type of surgery. We will also consider propensity score analysis to account for important confounding.

**Aim 6:** *To determine whether depth of anesthesia in frail patients is a modifiable risk factor for delirium and functional decline after cardiac surgery.*

In **Aim 6**, we will compare cumulative time of BIS<45 in frail vs. non-frail patients using bivariable and multivariable linear regression. The cumulative time of BIS<45 will also estimate the amount of potential anesthetic overdose in all patients.

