As of June 2016, we have enrolled 280 patients in the first five years and 244 patients in the second five year study. We need approximately 150 patients to complete enrollment.

In addition, we calculated the minimal sample size required to detect 0.2 SD difference in combined Z-score for cognitive tests normalized to the control group's data between the Intervention and Control groups with 80% power. We assume 2 follow-up points (4 to 6 weeks and 1 year after surgery) and an average within-patient correlation of 0.7 (observed in our preliminary data). The calculations indicate that we will need 177 observations per group, or 354 patients in total, to detect 0.2 SD difference with 80% power (assuming 5% Type I error). The study (first and second funding periods) will recruit a total of 489 patients to meet the MRI endpoint. Therefore, we will meet our goal of having 354 patients to detect the expected 0.2 SD difference in combined cognitive scores even with a 1-year drop-out rate as high as 27%. Historically, the drop-out rate for cognitive testing at 1 year in similar populations has been between 3% and 24%.

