## Statistical Analysis Plan

Tabular and graphical methods of data exploration will be used to evaluate variable distributions over the perioperative time period. When conducting modeling, we will determine the influence of the outliers on model fit. If the influence is high, we will consider excluding the outlier/s. We will explore the extent to which CBF autoregulation changes over the perioperative period. Univariate distributions for all study variables will be evaluated. We will explore potential confounders as variables strongly predictive of the outcomes (a priori and in the data) and differentially distributed between the study arms. Results of these analyses will be used to refine the analyses and guide model building and selection.

The cognitive outcome will be assessed as change from baseline in a composite cognitive Z score 4 to 6 weeks after surgery. The Z score will be calculated for individual tests at each testing time point with the mean and SD of baseline tests of all patients. Timed tests will be multiplied by '-1' so that higher scores represent better performance. Individual Z scores will be combined into an average Z-score, calculated from the average of the non-missing individual test Z-scores. These will then be renormalized using the mean and standard deviation at baseline. A difference between pre- and post-test  $> 0.3$  is considered cognitive decline.

Early stopping rules: N/A

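### Aim 1b is worded as a frequency of cognitive decline at 1 year, but its planned analysis and its power calculation concern a composite Z-score over both follow-ups

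*Combined protocol and SAP*

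**What the plan says.** The Objectives and Study Statistics word Aim 1b identically: whether the intervention "reduces the frequency of cognitive decline 1 year" after surgery, relative to usual pressure management.

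Under Study Statistics, the cognitive test scores are converted to Z-scores, and "The individual Z-scores will be combined into an average score and re-normalized". The Aim 1b analysis follows at once: "To assess postoperative change in cognitive function for up to 1 year (Aim 1b), we will use population-average marginal models", fitted by GEE with an exchangeable working correlation. Time enters as two indicators (4 to 6 weeks, 1 year) with baseline as reference. Time, group and "their interaction to test whether postoperative trajectory of cognitive function differs by group" make up the model.

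The sample size text, which sits after Rapid Dissemination of Clinical Research, seeks the number needed "to detect 0.2 SD difference in combined Z-score for cognitive tests". It assumes two follow-up points, a within-patient correlation of 0.7, 80% power and 5% type I error, and arrives at 177 per group (354 in total).

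Decline as a yes/no outcome is defined twice:
- The Neurocognitive Function text requires a drop of at least 1 SD on two or more tests, or 2 SD on one.
- The Statistical Analysis Plan, writing about 4 to 6 weeks, says that a pre-to-post difference above 0.3 in composite Z "is considered cognitive decline".

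**The concern.** The aim, read literally, compares two proportions at one time point. The analysis compares mean trajectories over two time points, and the sample size is set for a mean difference. These can disagree. A shift in the mean does not by itself show that fewer patients declined, and no difference in means does not exclude a difference in the proportion below a cut.

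If the plan is followed as written, the report will contain no pre-specified estimate of the quantity named in Aim 1b, and the 80% power could be quoted for a question it was not computed for. If a 1-year proportion were added later, two incompatible definitions would be available, and the choice could be made after the data are seen.

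**Working it through.** **1. Is there a 1-year comparison of proportions anywhere?** The two-sided test of proportions and the Poisson relative-risk model in Study Statistics are for the primary composite, whose cognitive component is at 4 to 6 weeks. Aim 4 plans a relative risk for delirium. Missing data adds random-effects and pattern-mixture versions of the longitudinal model. None of these compares decline frequency at 1 year.

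**2. Is the GEE outcome continuous?** The text gives no family or link, so this is an inference. It rests on three facts: the averaged Z-score is defined in the sentences just before; baseline is a level of the time factor, and decline from baseline cannot exist at baseline; and the power calculation is in SD units.

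**3. Reproducing 177 per group.** Inputs from the sample size text: δ = 0.2 SD, ρ = 0.7, power 80%, α = 5% (sidedness is not stated there; two-sided is used, as for the primary test). Formula: n per group = 2f[(1.960 + 0.842)/δ]², where f is the variance factor under a common correlation.

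| Quantity compared | f | n per group |
|---|---|---|
| Change from baseline to the mean of both follow-ups | (1+ρ)/2 + 1 − 2ρ = 0.45 | 176.6, so **177** |
| Mean of both follow-ups, baseline ignored | (1+ρ)/2 = 0.85 | 334 |
| Mean of both follow-ups, baseline-adjusted | (1+ρ)/2 − ρ² = 0.36 | 142 |
| Change from baseline to 1 year only | 2(1−ρ) = 0.60 | 235.5, so **236** |
| 1 year only, baseline-adjusted | 1 − ρ² = 0.51 | 201 |

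Of these, only the first matches. The arithmetic is sound, but the quantity is a mean averaged over 4 to 6 weeks and 1 year.

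**4. Power of the 1-year mean contrast at 177 per group.** 0.2/√(2 × 0.60/177) − 1.960 = 0.469, and Φ(0.469) = 68%.

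**5. Illustrative power for proportions.** The documents give no 1-year decline rate. Detection of Brain Injury quotes 18% to 40% across criteria and timings, and adds that most patients are back near baseline by 3 to 6 months, so 10% is included. The 40% relative reduction is borrowed from the primary composite. The test is two-sided at 5%, with pooled variance and no continuity correction. The last column takes the planned 630 patients with 27% to 24% dropout: 630 × 0.73/2 ≈ 230 and 630 × 0.76/2 ≈ 239 per arm.

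| Control vs intervention | 177 per arm | 230–239 per arm |
|---|---|---|
| 10% vs 6% | 28% | 35–36% |
| 18% vs 10.8% | 49% | 59–61% |
| 25% vs 15% | 65% | 77–78% |
| 30% vs 18% | 75% | 86–87% |
| 40% vs 24% | 90% | 96–97% |

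**6. Translating the powered effect into decliners.** Assume normal change scores with SD √0.60 = 0.775, the 0.3 cut, a 0.2 SD shift, and control mean change of −0.2, 0 or +0.2. The rates are then 44.9% vs 34.9%, 34.9% vs 25.9%, or 25.9% vs 18.3%. Power at 177 per arm is 48%, 45% or 41%.

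**The case against.** The continuous analysis looks deliberate. In Neurologic Outcomes after Cardiac Surgery the investigators warn that some common cut-off rules inflate decline rates, and they prefer regression models of the scores. The GEE, its random-effects and pattern-mixture companions and the power calculation all fit together, and only the word frequency is out of line. This stands, and it makes rewording the aim a sensible repair.

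A reader might infer that Aim 1b is never tested, or that 1-year cognition goes unanalysed. The documents do not support that. The GEE is labelled for Aim 1b, and its 1-year-by-group coefficient is a randomised comparison of mean change at 1 year. What is missing is the comparison of frequencies.

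A reader might also infer that the aim is underpowered. That is not established. The 177 is a minimum, not the expected 1-year number. The sample size text gives recruitment as 489 in one place (489 × 0.73 = 357, consistent with 354) and 630 in another. With 630 and 24% to 27% dropout, even the 1-year mean contrast reaches about 79% to 81% power by the formula in step 4 with 230 to 239 per group.

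Finally, the Neurocognitive Function definition is not limited to 4 to 6 weeks and could be applied at 1 year. That is so, but no between-group comparison is attached to it, and it conflicts with the 0.3 rule.

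**Conclusion.** The point holds as a mismatch between a stated secondary aim, its analysis and its power. Following the plan would support a conclusion about mean cognitive trajectory, not about the frequency of decline at 1 year.

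The firm figures are these: 177 per group corresponds to mean change averaged over both follow-ups, and the same inputs give about 68% power, or 236 per group for 80%, for mean change at 1 year alone. Both rest on the plan's correlation of 0.7 and a two-sided 5% test.

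The power figures for proportions are illustrative only, since both the control rate and the reduction are assumed. They show that the 80% cannot be carried over, not what the true power is. The reading of the GEE outcome as continuous is a strong inference rather than a statement in the text. The primary test and its sample size are not affected.

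**What to change.** Choose one of two routes before the data are analysed.

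1. **Align the aim with the analysis.** Reword Aim 1b, in the Objectives and in Study Statistics, as mean change in composite Z from baseline to 1 year. State the GEE outcome, family and link, name the 1-year-by-group coefficient as the test, and restate the power for that contrast using one consistent figure for expected 1-year numbers.
2. **Keep the frequency wording.** First settle which of the two decline definitions applies. Then add a 1-year relative risk of decline, using the Poisson model with robust standard errors already planned for Aim 1. State its own power with an explicit assumed control rate, and keep the Z-score model as supportive.

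The first route costs wording and one recalculation. The second adds one model. Both use the 1-year cognitive testing already scheduled in the Neurocognitive Function text.
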